Subconjunctival Injection of Local Anesthetic in Anterior Blepharoptosis Repair: Study Protocol and Statistical Analysis

Investigators: [name], [name]

Status: Recruiting

Document Date: June 6th, 2022

Study Start Date: September 1st, 2017

Anticipated Completion Date: June 2023

Sponsor: The University of Manitoba

Ethics Approval: The University of Manitoba Bannatyne Campus Biomedical Research Ethics Board. Affiliated with the University of Manitoba. Approval Number: HS20066 (B2016:085). Address: [name].

Study Design: Single group interventional study. Randomized allocation. 100 participants anticipated (200 eyes). Patients to receive two subconjunctival injections each (one to each eye), giving two study arms (intervention vs. sham).

Participants will be recruited from [name] patient population. They will include those who have elected to undergo bilateral ptosis repair and participate in the study. They must meet the following inclusion criteria in order to be deemed eligible to participate:

1. Age over 18 and able to provide informed consent in English.
2. Must have bilateral blepharoptosis undergoing repair using an anterior approach.
3. The degree of ptosis must be approximately symmetrical, with a difference in "Margin Reflex Distance one (the distance between the pupillary light reflex and the margin of the upper lid)" of 1 mm or less between the two sides.

Participants will be excluded if they meet the following criteria:

1. Previous eyelid surgery or trauma.
2. Have congenital, mechanical, myogenic, or neurogenic form of ptosis.
3. Bleeding disorder or inability to discontinue anti-coagulants pre-operatively.
4. Cognitive impairment

After learning about the risks and benefits of participation, each patient will sign an informed consent form on the day of their surgery. Each patient will then receive an intra-operative posterior subconjunctival injection in both eyes. One injection will contain xylocaine (a local anesthetic) while the other will contain normal saline (a sham injection). All surgeries will be performed by [name]. Both the participants as well as [name] will be blinded as to which eye receives the intervention and the sham injection.

Post-operatively, patients will be asked to complete a pain scale questionnaire immediately following their surgery. Specifically, they will be asked to compare their pain in each eye. The results of this assessment will be compared using McNemar's Test, and will constitute the primary outcome of the study. The secondary outcomes will include:

1. The presence or absence of post-operative lagophthalmos/fluorescein staining, as assessed at the post-operative follow-up. Comparison between the xylocaine injection group and the normal saline injection group will be performed using McNemar's Test.
2. Post-operative "Margin Reflex Distance One" (as described above) will be compared between the xylocaine injection group and the normal saline injection group. The difference between the two groups will be evaluated using a Paired Student's T-Test.

Surgical procedures will be performed at the Buhler Eye Care Centre, Misericordia Hospital, [name].

Data will be intermittently reviewed by [name] throughout the study period.

This study has received Ethics Approval from the University of Manitoba: HS20066 (B2016:085).

Page 2 of 2

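### Should the primary McNemar test of between-eye pain give way to an order-adjusted test because one eye is probably finished before the other?

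*Protocol*

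**What the plan says.** The design is within-patient. In the intervention paragraph on page 1 of the protocol, "Each patient will then receive an intra-operative posterior subconjunctival injection in both eyes", xylocaine on one side and saline on the other, with allocation described as randomised under Study Design. In the same paragraph, "All surgeries will be performed by" one person, whose name is removed.

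For the primary outcome (page 2), "patients will be asked to complete a pain scale questionnaire immediately following their surgery", and more specifically "they will be asked to compare their pain in each eye". The analysis is fixed in the next sentence: "The results of this assessment will be compared using McNemar's Test, and will constitute the primary outcome of the study".

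The protocol does not state which eye is operated on first, the interval between eyes, or whether order is recorded. It gives no expected drug effect, no expected share of patients reporting equal pain, and no power statement. It anticipates 100 participants. Its header gives "Study Start Date: September 1st, 2017" and "Anticipated Completion Date: June 2023".

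**The concern.** With one operator and two lids, one repair very probably ends before the other. That is an inference, but a reasonable one. When pain is compared once at the end, the two eyes then differ in time since surgery, and perhaps in time since injection. If patients tend to find the same position worse (say, the eye finished last), this tendency sits in the primary comparison alongside the drug effect.

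Two things might be at stake. One is validity, if order could pass for a drug effect. The other is power: McNemar's test pools patients over order and treats the order tendency as noise, whereas an order-adjusted paired test removes it. Since the protocol itself names the test, the point is not merely a detail left to a later analysis plan.

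**Working it through.** There is no stated power to reproduce. The inputs below are assumptions, except the 100 patients and the paired test, which come from the protocol.

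**Model.** Two-sided 5%; drug log-odds 0.6; θ = logit(p), where p is the share of patients who would find the same position worse without any drug effect (50, 60, 70, 80%); each patient's xylocaine eye chosen at random, independently of order.

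**Step 1: validity.** With no drug effect, the chance that the saline eye is called worse is ½p + ½(1 − p) = 0.5 for every p. Uncorrected McNemar with n = 100 rejects when (2b − 100)²/100 > 3.84, that is b ≥ 60 or b ≤ 40. Under Bin(100, 0.5) this has probability 5.7%; with n = 50 (b ≥ 32 or b ≤ 18) it is 6.5%. The excess over 5% comes from discreteness and not from order. If order is forced into exact balance and McNemar is kept, the size falls (n = 100: 3.8% at p = 70%, 1.7% at 80%), which is conservative.

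**Step 2: power without ties.** The share calling the saline eye worse is π = ½[expit(θ + 0.6) + expit(0.6 − θ)]:

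- p = 50%: ½(0.646 + 0.646) = 0.646
- p = 60%: ½(0.732 + 0.549) = 0.640
- p = 70%: ½(0.810 + 0.439) = 0.624
- p = 80%: ½(0.879 + 0.313) = 0.596

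McNemar power follows from Bin(n, π) and the rejection regions in Step 1. Mainland-Gart power (a 2×2 chi-square of order group by the eye called worse) is from simulation.

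| p | McNemar, 100 pairs | Mainland-Gart, 100 pairs | McNemar, 50 pairs | Mainland-Gart, 50 pairs |
|---|---|---|---|---|
| 50% | 85.5% | 84.4% | 60% | 56% |
| 60% | 82.8% | 82.6% | 57% | 54% |
| 70% | 72.7% | 77.5% | 47% | 48% |
| 80% | 51.2% | 66.2% | 32% | 38% |

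So a useful gain appears only from about 70% with 100 informative pairs. With 50 pairs, the tests as they would actually be run differ by about 1 point at 70%, and adjustment loses about 3 points at 50 to 60%. Part of that loss reflects McNemar running above 5%: with both tests calibrated to exactly 5%, the differences at 50 pairs are about -0.5, +1, +6 and +11 points.

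**Step 3: power with ties.** Patients asked to compare two eyes may report no difference. Both standard order-adjusted choices (Mainland-Gart, and conditional logistic regression with an order term) drop those patients, as McNemar does. Take a latent logistic response with a tie zone, 100 patients in all, and p now the share among patients with a preference. All sizes are close to 5%. Power, McNemar vs Mainland-Gart:

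| Ties | p = 70% | p = 80% |
|---|---|---|
| about 20% | 82.0 vs 83.2% | 67.5 vs 72.2% |
| about 40% | 84.8 vs 84.0% | 77.4 vs 73.9% |
| about 60% | 82.0 vs 78.8% | 77.7 vs 68.7% |

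The sign of the difference turns with the tie rate. Where ties are common, the replacement is worse in just the range where it was meant to help.

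**Step 4: a version that keeps ties.** A Prescott-type test compares the three-level answer (first eye worse, no difference, second eye worse) between order groups. Against McNemar it gives about 77 vs 73% (no ties) to 84 vs 82% (about 60% ties) at p = 70%. At p = 80% it gives about 66 vs 51% to 83–84 vs 78%. At 50 to 60% the two are within about 1.5 points.

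**Step 5: timing.** From September 2017 to the document date of June 2022 is 57 months, and to the anticipated completion 69 months. 57/69 = 83% of the planned period had passed.

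**The case for a change.** The best case for a change runs as follows. The protocol fixes the test, so the choice is open to comment. Adjustment costs one data field and one sentence. It loses at most about 1.5 points if order does not matter (100 patients, tie-retaining form), and it can recover up to about 15 points if order matters a great deal. The trial is still recruiting, so the change could be specified before unblinding.

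The efficiency argument stands, as a conditional statement. It does not carry a change of primary test. Nothing in the protocol indicates that order affects pain, let alone at 70:30 or beyond, and the sequence itself is inferred. The usual adjusted tests can lose power, depending on a tie rate nobody has stated. The tie-retaining form avoids that, but it needs operating order for patients enrolled since 2017, and the protocol does not say order was collected. It would also replace a named primary test late in a trial whose data are reviewed from time to time, which invites doubt about why it was changed.

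One condition deserves stating. Validity rests on the xylocaine eye being randomised independently of order. A systematic link would be serious: with a fixed 60/40 split of drug over order and p = 70%, exact McNemar would reject 7.8% of the time under the null. The protocol calls the allocation randomised, and nothing in it suggests such a link.

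**Conclusion.** No change to the plan. McNemar's test is a standard, valid test for a binary within-patient comparison with the drug randomised to eye. Ignoring operating order is an efficiency trade-off and not an error.

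Under the assumptions used (drug log-odds 0.6, 100 patients, simple randomisation), the power forgone against the best order-adjusted alternative is practically nil when up to 60% of patients would find the same position worse. It is about 2 to 4 points at 70% and about 6 to 15 points at 80%, depending on ties. The more familiar adjusted tests range from about 15 points better to about 9 points worse at 80%.

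If operating order is in the surgical record, an analyst may report an order-adjusted, tie-retaining sensitivity analysis beside the McNemar result. That would inform the reader without altering the primary conclusion, and the protocol need not be amended for it. The judgement would change only with evidence of a strong order effect, or of an allocation tied to operating order. The protocol offers neither.

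### Does the undefined slash in lagophthalmos/fluorescein staining leave secondary outcome 1 without a usable analysis?

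*Protocol*

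**What the plan says.** The Protocol (page 2, list of secondary outcomes, item 1) gives the outcome as "The presence or absence of post-operative lagophthalmos/fluorescein staining, as assessed at the post-operative follow-up". The analysis sentence follows directly: "Comparison between the xylocaine injection group and the normal saline injection group will be performed using McNemar's Test". Neither sign is mentioned again, so no other text says how the slash is to be read.

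The Study Design paragraph on page 1 supplies the pairing: "Patients to receive two subconjunctival injections each (one to each eye), giving two study arms (intervention vs. sham". It plans for 100 patients and 200 eyes, hence 100 within-patient pairs.

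Two further statements bear on timing. The header reads "Study Start Date: September 1st, 2017" in a document dated June 2022 with recruitment still open. Near the end, page 2 says "Data will be intermittently reviewed by" a person whose name has been removed. For this outcome the document states no event rate, significance level or power.

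**The concern.** McNemar's Test needs each eye coded yes or no. Take an eye with staining but no lagophthalmos. It is positive if either sign suffices, negative if both are required, and positive on one outcome and negative on the other if the signs are analysed separately. The protocol does not say which applies.

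If a single combined outcome were intended, two things could go wrong. A real difference in one sign could be diluted by a sign that does not differ, and a significant result could not be attributed to either sign. A non-significant combined result would also not show that lagophthalmos alone, or staining alone, was similar in the two eyes. Finally, the study began in 2017 and its data are looked at from time to time, so an open definition leaves room for the reading to be settled after results are known.

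**Working it through.** **There is no planned figure to reproduce.** The only arithmetic in the document is 100 patients × 2 eyes = 200 eyes, which is consistent. All rates and counts below are assumptions.

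**1. Can the reading change the counts?** Take an invented set of 100 pairs in which no pair has a sign in both eyes:

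- lagophthalmos only: 14 pairs in the xylocaine eye, 4 in the saline eye
- staining only: 5 xylocaine, 12 saline
- both signs in one eye: 1 xylocaine, 2 saline
- neither sign: 62 pairs

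The exact McNemar p-value is twice the smaller binomial tail of the discordant pairs at probability 0.5.

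| Reading | Xylocaine only | Saline only | p |
|---|---|---|---|
| Lagophthalmos alone | 14 + 1 = 15 | 4 + 2 = 6 | 0.078 |
| Staining alone | 5 + 1 = 6 | 12 + 2 = 14 | 0.115 |
| Either sign | 14 + 5 + 1 = 20 | 4 + 12 + 2 = 18 | 0.871 |
| Both signs | 1 | 2 | 1.00 |

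The counts differ, and the either-sign outcome hides two opposite trends. No row falls below 0.05, so in this set the formal conclusion is the same on every reading. The reading can change the conclusion but need not.

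**2. How much power could a combined outcome lose?** The inputs are a simulation of 100 pairs with between-eye correlation 0.5, between-sign correlation 0.2 and a two-sided 0.05 test. Lagophthalmos is set at 20% v 8%, and staining at 25% in both eyes. Power is by chi-square McNemar, with exact in brackets. The last column puts the expected discordant counts b and c into (b − c)² / (b + c), for comparison with the critical value 3.84.

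| Reading | Expected discordant pairs | Power | (b − c)² / (b + c) |
|---|---|---|---|
| Lagophthalmos alone | 15.7 v 3.7 | 82% (75%) | 12.0² / 19.4 = 7.42 |
| Either sign | 20.6 v 12.4 | 30% (23%) | 8.2² / 33.0 = 2.04 |
| Both signs | 6.0 v 2.1 | 25% (15%) | 3.9² / 8.1 = 1.88 |

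The loss has a simple source. In each eye, the either-sign rate plus the both-sign rate equals the sum of the two single rates. The net difference of 12 pairs (20 − 8) is therefore shared between the two combined outcomes: 8.2 + 3.9 = 12.1, which agrees apart from rounding. With staining equal in both eyes at 5% to 40% and between-sign correlation 0.2 to 0.8, power runs from 6% to 70% for either sign and from 4% to 70% for both.

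**3. Does it always lose?** No. Let staining shift as well and keep lagophthalmos at 20% v 8% (82% alone):

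| Staining | Between-sign correlation | Power, either sign |
|---|---|---|
| 25% v 13% | 0.2 | 94% |
| 25% v 13% | 0.8 | 85% |
| 30% v 18% | 0.2 | 90% |
| 30% v 18% | 0.8 | 79% |

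The either-sign outcome does better than lagophthalmos alone in three of the four cases. Since the protocol gives no rates, the sign of the effect on power cannot be known.

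**4. What would separate testing cost?** With two tests at 0.05 each, the chance of at least one false positive is 1 − 0.95² = 0.0975 under independence, and at most 0.05 + 0.05 = 0.10 in general. For a pair of secondary outcomes that is a modest price. It means that neither approach is better on every count.

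**5. What does the text fix?** It fixes the two signs, a yes/no scale, the visit, the within-patient comparison and the method. It does not say that one test is run, and it does not call the item a composite. The dilution and attribution problems arise only if a composite was meant, and nothing in the document shows that.

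**The case for a change.** The strongest argument for a change is that what counts as an event is part of the outcome's definition and is more than an analysis detail. The document's title covers statistical analysis as well as the protocol, and it names the test for this item without naming the event that the test counts. One clause would settle the matter at almost no cost, and a clause dated before unmasking would remove any doubt about a choice made with results in view.

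Part of this stands. The slash is undefined, and a clarifying clause would do no harm.

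The rest carries less weight. Following the plan as written has not been shown to produce a wrong result: on the separate reading the analysis is complete, and only the wording is loose. How two signs listed on one line are coded and tabulated is commonly settled in the case report form or the statistical analysis plan, which may exist but is not shown. The remark about data review does not say that outcomes are seen by arm, and page 1 states that the patients and one named person are blinded. The dates and the review are therefore context and do not show a results-driven choice.

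**Conclusion.** No change to the plan is called for. The ambiguity is real but small: an unwritten coding rule for one secondary outcome, which an analyst would fill by tabulating each sign by eye and applying McNemar's Test to each. The test suits paired binary data however the slash is read. The illustrative power figures go both ways (30% or 25% against 82% in one scenario, 94% against 82% in another) and rest wholly on assumed rates and correlations, so they do not show that separate outcomes beat a combined one.

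This conclusion assumes that both signs were recorded separately for each eye, which the protocol does not state. If only a combined result was recorded for some patients, those patients could not be split and the report would have to say which rule was used. The primary pain comparison and the paired t-test of Margin Reflex Distance One do not depend on any of this.

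### The paired t-test on post-operative MRD1 is valid but ignores the pre-operative difference between the eyes, which may cost some precision

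*Protocol*

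**What the plan says.** - **Analysis (Protocol, secondary outcome 2).** Post-operative MRD1 "will be compared between the xylocaine injection group and the normal saline injection group", and "The difference between the two groups will be evaluated using a Paired Student's T-Test". Neither a covariate nor a change from baseline is mentioned.
- **Eligibility (Protocol, inclusion criterion 3).** Ptosis must be roughly symmetrical, with an MRD1 difference "of 1 mm or less between the two sides".
- **Design (Protocol, Study Design and the paragraph on the injections).** "Randomized allocation. 100 participants anticipated (200 eyes"; each patient has both injections: "One injection will contain xylocaine (a local anesthetic) while the other will contain normal saline (a sham injection".
- **Data review (Protocol, page 2).** "Data will be intermittently reviewed by" a person whose name is removed, throughout the study period.

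**The concern.** Criterion 3 requires a comparison of the two sides' MRD1 before surgery in every patient, and the same measure is then an outcome after surgery. In the xylocaine-minus-saline direction, the pre-operative difference can lie anywhere from -1 to +1 mm. If part of it survives the bilateral repair, that part stays in the post-operative paired difference as noise, although a measured baseline could explain it.

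The MRD1 comparison is how the trial judges whether the injection alters lid height. A tighter interval would make either conclusion firmer, that it does or that it does not. The stake is limited: this is the second of two secondary outcomes, and no bias is involved.

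**Working it through.** **Inputs.** From the Protocol: n = 100 patients, one eye per treatment, randomised allocation, pre-operative difference within ±1 mm. The Protocol gives no alpha, power, SD, MRD1 effect or correlation. The figure of 100 therefore cannot be reproduced; it is not disputed and is used only as n. All SDs, correlations and effects below are assumptions.

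**Model.** Let D0 be the pre-operative and Y the post-operative within-patient difference (xylocaine eye minus saline eye):

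Y = δ + b·D0 + e

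Here b is the share of asymmetry that persists and e is residual noise.

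**Step 1: validity.** Randomising which eye gets xylocaine makes the expected D0 zero, so the mean of Y estimates δ whatever b is. A simulation (20,000 trials per setting, 100 pairs, D0 uniform on -1 to 1 mm, residual SD 0.75 mm, two-sided 5% level) gave a type I error of 4.7% to 5.1% for b = 0, 0.25, 0.5 and 1. This held for the paired t-test and for the regression intercept alike.

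**Step 2: standard error by correlation.** With ρ the correlation between D0 and Y,

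SE(adjusted)/SE(paired t) = √[(1 − ρ²)(1 + 1/(n − 3))] = √[(1 − ρ²) × 98/97]

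| ρ | Ratio | Change in SE |
|---|---|---|
| 0 | 1.0051 | +0.5% |
| 0.1 | 1.0001 | 0.0% |
| 0.2 | 0.9848 | -1.5% |
| 0.3 | 0.9588 | -4.1% |
| 0.5 | 0.8705 | -13.0% |

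Break-even is at ρ = √(1 − 97/98) = 0.101.

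**Step 3: standard error by persistence.** Here ρ = b × SDpre/SDpost. Assume SDpre of 0.41 mm (triangular on ±1 mm) to 0.58 mm (uniform on ±1 mm), and SDpost of 0.6 to 1.0 mm.

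- b = 0: ρ = 0, change +0.5%.
- b = 0.25: ρ runs from 0.25 × 0.41/1.0 = 0.10 to 0.25 × 0.577/0.6 = 0.24; change 0% to -2.4%.
- b = 0.5: ρ runs from 0.5 × 0.41/1.0 = 0.205 to 0.5 × 0.577/0.6 = 0.48; change -1.6% to -11.9%.

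**Step 4: cross-check by power.** The simulation of step 1 fixes the residual SD (0.75 mm) instead of the total SD. With an assumed true difference of 0.2 mm:

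| b | Paired t | Regression intercept | Change score |
|---|---|---|---|
| 0 | 75.4% | 75.1% | 56.0% |
| 0.25 | 73.9% | 74.7% | 62.8% |
| 0.5 | 69.7% | 74.9% | 69.3% |
| 1 | 55.5% | 74.7% | 75.3% |

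The difference detectable with 80% power, (1.96 + 0.84) × SD/√100, is 0.210 mm adjusted. Unadjusted it is 0.214 mm (b = 0.25), 0.225 mm (b = 0.5) or 0.265 mm (b = 1).

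**Step 5: why not a change score.** Its variance is SDpost² + SDpre²(1 − 2b), which exceeds SDpost² whenever b < 0.5. At b = 0.25 with the SDs of step 3:

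- smallest loss: √[(1.0 + 0.1667 × 0.5)/1.0] = 1.04, an SE 4% larger;
- largest loss: √[(0.36 + 0.3333 × 0.5)/0.36] = 1.21, an SE 21% larger.

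**The case against.** The strongest reply is that nothing is wrong: a paired test is stated for paired eyes under randomised allocation, and preferring a regression is taste. The symmetry criterion already caps the problem, and nothing in the Protocol shows that asymmetry survives repair of both lids. Even the sign of the gain is open. The -13.0% at ρ = 0.5 needs b of at least 0.5 × 0.6/0.577 = 0.52 under the SDs assumed here. An unseen SAP might add an adjusted analysis. The signed per-eye values are not said to be stored. Recruitment began in September 2017 and completion is expected in June 2023, so changing a stated analysis now invites suspicion of a data-driven choice.

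Most of this stands, and it sets the weight of the point. The planned test is not an error, the missing adjustment is not an omission, and the gain may be nil. What remains is that the Protocol itself names the unadjusted test while its own eligibility rule requires the relevant baseline comparison. The trade is also lopsided: about 0.5% in SE if nothing persists, against up to about 12% saved if half does. The objections on data availability and timing are met by conditions on the fix.

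**Conclusion.** The point holds as a minor matter of efficiency. The unadjusted paired t-test is valid and unbiased, and precision is lost only if pre-operative asymmetry persists after repair. The loss is nil if none persists, small if a quarter does, and material only if about half or more does. Persistence and both SDs are assumptions, so the Protocol cannot say which case applies. The 1 mm limit bounds the loss, because the SD of the pre-operative difference cannot exceed 1 mm. Confidence that the change would bring a worthwhile gain is moderate at best.

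**What to change.** Prespecify, before any unblinded analysis, a linear regression of the post-operative MRD1 difference (xylocaine eye minus saline eye) on the pre-operative difference taken in the same direction, using the values measured for eligibility. Report the intercept, which is the effect at zero pre-operative difference, with its 95% CI as the treatment effect. Keep the paired t-test as a sensitivity analysis, and do not substitute a simple change score.

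The cost is one degree of freedom, about 0.5% in SE if the correlation is zero, and no extra patients or visits. Two conditions apply:

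- **Data.** Signed per-eye pre-operative MRD1 must exist as study data or be recoverable from the surgical chart. If not, leave the paired t-test as it is.
- **Timing.** Because recruitment is long under way and data are reviewed along the way, make the change by a dated amendment stating that it preceded any sight of unblinded MRD1 results.

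### Should the paired t-test for post-operative MRD1 have included a term for which eye received xylocaine?

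*Protocol*

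**What the plan says.** The Study Design paragraph describes a within-patient comparison: "Patients to receive two subconjunctival injections each (one to each eye), giving two study arms (intervention vs. sham"). Allocation is randomised, with 100 participants (200 eyes) anticipated. The paragraph on the injections confirms the pairing: "One injection will contain xylocaine (a local anesthetic) while the other will contain normal saline (a sham injection"). Masking concerns the eye, since those masked "will be blinded as to which eye receives the intervention and the sham injection". What can be randomised is therefore which eye gets xylocaine. The protocol does not spell this out, nor how right and left are balanced.

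Inclusion criterion 3 limits the MRD1 difference between the two sides to 1 mm.

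Under secondary outcome 2, post-operative MRD1 "will be compared between the xylocaine injection group and the normal saline injection group", and the method is fixed in one sentence: "The difference between the two groups will be evaluated using a Paired Student's T-Test". No SD, effect size, alpha or power is given for MRD1, and no side term is named.

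**The concern.** Random allocation of the side creates two sets of patients, those with xylocaine on the right and those with xylocaine on the left. If right lids end up higher or lower than left lids by S on average, the xylocaine-minus-saline difference carries +S in one set and −S in the other. A plain paired t-test cannot separate this pattern from random scatter, so S inflates the error variance.

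The allocated side must be on record to identify which eye had which injection, so a model could remove this component without new data. What would be at stake is precision: an MRD1 interval wider than necessary and some lost power.

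**Working it through.** The protocol gives no MRD1 figure to reproduce, so the check is of validity first and then of size.

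**Inputs.** n = 100 pairs (Study Design). Assumed, because the protocol gives none: SD of the within-patient difference σ = 0.7 mm, treatment effect τ = 0.2 mm, two-sided alpha 5%, and S = 0, 0.1, 0.25 and 0.5 σ (0, 0.07, 0.175 and 0.35 mm).

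**Model.** For each patient D = τ + s·S + e, with s = +1 or −1 by allocated side and e of SD σ.

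**Bias.** With 1:1 randomisation the mean of s is zero in expectation, so the mean of D estimates τ whatever S is.

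**Variance.** The plain test works with σ² + S²; a regression of D on side works with σ². The ratio of standard errors is √(1 + (S/σ)²):

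- S = 0.1 σ: √1.01 = 1.005
- S = 0.25 σ: √1.0625 = 1.031
- S = 0.5 σ: √1.25 = 1.118

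At σ = 0.7 mm the unadjusted standard errors are 0.070, 0.072 and 0.078 mm, against 0.7/√100 = 0.070 mm.

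**Type I error and power**, from 200,000 simulated trials per setting; power is plain / side-adjusted:

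| S | Power, balanced sides | Power, simple allocation | Type I error of plain test, balanced |
|---|---|---|---|
| 0 | 80.9 / 80.9% | 80.8 / 80.5% | – |
| 0.1 σ | 80.5 / 80.8% | 80.5 / 80.5% | 4.9% |
| 0.25 σ | 78.9 / 80.6% | 78.4 / 80.4% | 4.3% |
| 0.5 σ | 73.6 / 80.8% | 71.6 / 80.4% | 2.8% |

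Under simple allocation the type I error is about 5% for both analyses. Under exact balance the plain test errs only on the conservative side. The plain analysis is therefore valid in every setting tried.

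**The side term is not free.** Under simple allocation, chance imbalance of sides multiplies the variance of the adjusted estimate by E[1/(1 − s̄²)] = 1.0103 at n = 100. The two analyses break even where (S/σ)² equals the excess, so S/σ = √0.0103 ≈ 0.10. With 75 and 50 patients the factors are 1.0139 and 1.0213, giving 0.118 and 0.146. Below these values the side-adjusted estimate is slightly the less precise one.

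**Other SDs.** With σ from 0.5 to 1.0 mm, take an effect that the adjusted analysis detects with 80% power. The plain test has 78.5 to 79.6% power at S = 0.1 mm and 50.9 to 70.8% at S = 0.5 mm.

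**How large S must be to matter.** At n = 100 the effect detectable with 80% power is 0.212 mm at σ = 0.75 mm, that is 0.212/0.75 = 0.283 σ. If S were as large as that effect, the variance factor would be 1 + 0.283² = 1.080. The noncentrality would fall from 2.83 to 2.83/√1.080 = 2.72, and power from 80% to about 77%. A loss well beyond 3 points thus needs a right-left difference larger than the effect the trial could detect.

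**The case for a change.** The best case for a side term is that the protocol names a specific test, in a document whose title covers statistical analysis, so this is a stated choice and not silence. Including side needs no new data and costs almost nothing if sides are balanced (one degree of freedom moves power from 80.77% to 80.76%). It could recover up to 9 power points in the largest case tabulated. The symmetry criterion does not rule S out: it caps the pre-operative difference in each patient but says nothing about its direction or the post-operative result.

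All of that is true. What it does not supply is a reason to think S is appreciable. S, σ, τ and the allocation method are all assumed. If S is near zero, which nothing in the protocol contradicts, the change gives nothing or makes precision marginally worse under simple allocation.

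There is also a cost beyond arithmetic. The study began in September 2017, the document is dated June 2022, and the protocol adds "Data will be intermittently reviewed by" before a removed name. Demoting the documented test at that stage would invite questions about post-hoc choice, for an unknown and possibly nil gain.

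**Conclusion.** The concern does not hold. A paired t-test is a standard and correct analysis of a continuous outcome measured on both eyes of each patient when the treated side is randomised. The protocol states nothing wrongly here, contradicts nothing and fixes nothing badly.

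Omitting side can cost only efficiency. Under the assumed 0.7 mm SD and 0.2 mm effect the cost is nil or negligible up to 0.1 SD, about 2 power points at 0.25 SD, and 7 to 9 points only at 0.5 SD (0.35 mm). Whether to add a side term is a matter on which reasonable statisticians would differ, and a separate analysis plan may already do so.

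The conclusion rests on the side really being randomised, as the Study Design paragraph implies. If xylocaine always went to the same side, the effect would be confounded with side and a side term could not rescue it. It covers the MRD1 comparison only; no calculation was made for the McNemar analyses.

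### Do the intermittent data reviews leave the type I error of the primary comparison unprotected?

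*Protocol*

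**What the plan says.** The protocol has no numbered sections. One sentence near the end of page 2 covers the reviews: "Data will be intermittently reviewed by [name] throughout the study period". It does not say which data are reviewed, how often, for what purpose, or with what consequence.

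Four other places bear on the point:

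- **Size.** The Study Design entry gives "100 participants anticipated (200 eyes").
- **Time.** The header gives "Study Start Date: September 1st, 2017" and "Anticipated Completion Date: June 2023". At the document date of 6 June 2022 it gives "Status: Recruiting".
- **Masking.** The paragraph after the exclusion criteria says that the participants and a person whose name has been removed "will be blinded as to which eye receives the intervention and the sham injection".
- **Analysis.** Each patient is their own control: "One injection will contain xylocaine (a local anesthetic) while the other will contain normal saline (a sham injection"). For the comparison of pain between the two eyes, page 2 says: "The results of this assessment will be compared using McNemar's Test, and will constitute the primary outcome of the study".

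The protocol states no significance level, interim analysis, stopping rule or sample size re-estimation.

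**The concern.** Three features together resemble a familiar fault. Accumulating data are looked at repeatedly over a long period. The sample size is worded as an expectation, so nothing obviously fixes when recruitment ends. The blinding statement does not mention the reviews.

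If the reviews showed pain results by treatment and the decision to stop or continue recruiting depended on them, the final McNemar p-value would no longer have its nominal error rate. The paired design would make such a look informative: with the allocation list, each patient's between-eye comparison points directly at the treatment effect. If the reviewer also operated or assessed outcomes, by-arm results could weaken the blind as well.

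**Working it through.** The protocol states no error rate or power, so there is no figure of its own to reproduce. The check compares what the text commits the study to with what would have to be true for the error rate to rise.

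**1. Duration.** From 1 September 2017 to June 2023 is 5.75 years (1 June) to 5.83 years (30 June). Nearly six years is right. At the document date the study had run about 4 years and 9 months and was still recruiting.

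**2. Error rate of the plan as written.** With *b* and *c* the two kinds of discordant pair, uncorrected McNemar rejects when (*b* − *c*)² / (*b* + *c*) > 3.84. The level is an assumption: two-sided 0.05. Overall type I error is the probability under the null hypothesis that at least one decision-bearing test rejects. A review with no test and no decision adds no chance to reject and does not change the number of patients analysed, so only the final test counts. By simulation, one test gives 0.050 under normal theory. With 100 patients and an assumed 30% to 100% of pairs discordant, it gives 0.050 to 0.058 for uncorrected McNemar and 0.030 to 0.038 for exact McNemar. The departures from 0.05 come from the discreteness of the test, not from the reviews.

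**3. Error rate under the feared scenario.** Assume *K* equally spaced by-arm tests, each at 0.05, with stopping at the first significant result. Under normal theory the statistic at look *k* is *Z*ₖ = (*X*₁ + … + *X*ₖ)/√*k*, and the overall error is P(|*Z*ₖ| > 1.96 for some *k* ≤ *K*). McNemar ranges are over the same assumed discordance, with 100 patients.

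| Looks *K* | Normal theory | McNemar, uncorrected | McNemar, exact |
|---|---|---|---|
| 2 | 0.083 | 0.083–0.101 | 0.050–0.062 |
| 3 | 0.107 | 0.101–0.110 | 0.061–0.088 |
| 5 | 0.142 | 0.138–0.145 | 0.076–0.106 |
| 6 | 0.155 | 0.153–0.156 | 0.080–0.132 |
| 10 | 0.194 | 0.172–0.196 | 0.093–0.143 |

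The inflation figures of 8.3% to 19.4% are therefore correct for that scenario under normal theory. The exact test gives clearly less.

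**4. Does the protocol describe that scenario?** It needs two things together: the reviews must reveal results by treatment, and they must influence when recruitment ends or what is analysed.

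- *Results by treatment.* The sentence speaks of data, not of outcomes by arm. It fits checks of completeness, consent, safety or record-keeping equally well.
- *Masking.* The reviewer's name and the blinded person's name are both removed from this copy. They may be the same person, in which case the protocol itself masks the reviewer. A gap made by removing names is not a gap in the plan.
- *Influence on recruitment.* No sentence lets a review stop the study, extend it or change its size. The word anticipated is attached to both the number of participants and the completion date. In a study still recruiting, it reads naturally as planned.

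Neither condition is stated.

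**The case for a change.** The strongest counter-argument is that this document presents itself as covering the statistical analysis as well as the protocol, and that it names a test for each outcome. On that view, the end of recruitment and access to by-arm results are matters of design and conduct that a protocol should settle. An unqualified licence to review data, beside a size that is only anticipated, then fails to exclude data-dependent stopping. Informal stopping needs no formal test to do harm, and even exact McNemar with five looks gives 7.6% to 10.6%. A clarifying sentence would cost little, and it would carry more weight before the final analysis than after it.

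Part of this stands. The sentence is thin, and a reader cannot tell from it what the reviews contain. Continued recruitment in June 2022 shows that no review had ended the study by then, but it does not show what the reviews were for.

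The rest does not follow. Not excluding a practice is different from planning it. Number of looks, boundaries and allocation of alpha are ordinary content of a statistical analysis plan, and one may exist unseen. Nor is the obvious remedy free: ending recruitment at 100 patients or June 2023, whichever comes first, would turn a forecast date into a hard stop and could leave fewer than the 100 patients intended, with a loss of power.

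**Conclusion.** The concern does not hold. Under the protocol as written, the reviews carry no test and no decision, about 100 patients are recruited, and one McNemar comparison is made for the primary outcome. Inflation of type I error from the reviews is then zero.

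This rests on reading the review sentence for what it says and on taking the anticipated 100 as the planned size. The 5% level is an assumption throughout, since the protocol gives none. If study records showed by-arm looks that could stop or prolong recruitment, the rates tabulated above would become relevant, but nothing in this document says so. The remaining uncertainty about the content and masking of the reviews comes from brevity, removed names and an analysis plan that is not shown; it is not an error in the plan.
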